##### 5.3.2.1. Definitions of Adverse Events

Solicited AEs shown in the tables will be extracted from the investigator assessment pages (CE) of the CRF. Solicited administration site symptoms by definition will be considered as related to the study vaccine.

The severity of the AEs will be classified as grade 1 to 4. Solicited events of grade 0, not reported in the CE domain, will therefore not be reported in the AE analysis.

In addition to the potential AESIs as identified by the investigator in the database, potential AESIs will also be selected programmatically. Those will include all reported AEs that are identified by the selection rule: SMQ (Standardised MedDRA Queries) = “EMBOLIC AND THROMBOTIC EVENTS (SMQ)” or (SUB\_SMQ1 = “HAEMATOPOIETIC THROMBOCYTOPENIA (SMQ)” and SCOPE in (“BROAD”, ”NARROW”)) or HLT (higher level term)=“Thrombocytopenias”.

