## 5.1. Inclusion Criteria

Each potential participant must satisfy all of the following criteria to be enrolled in the study:

1. must sign an informed consent form (ICF) indicating that the participant understands the purpose, procedures, and potential risks and benefits of the study, and is willing to participate in the study.
2. willing and able to adhere to the prohibitions and restrictions specified in this protocol.
3. aged 60 years or older on the day of signing the ICF and expected to be available for the duration of the study.
4. before randomization, a participant must be:
  - postmenopausal (postmenopausal state is defined as no menses for 12 months without an alternative medical cause); and
  - not intending to conceive by any methods.

*Note: Surgically sterile participants are also eligible for the study.*

5. in the investigator's clinical judgment, participant must be in stable health at the time of vaccination. Participants may have underlying illnesses such as hypertension, congestive heart failure, COPD, Type 2 diabetes mellitus, hyperlipoproteinemia, or hypothyroidism, as long as their symptoms and signs are stable at the time of vaccination, and these conditions receive routine follow-up by the participant's healthcare provider. Participants will be included on the basis of physical examination, medical history, and vital signsa performed between ICF signature and vaccination.
6. For participants in Cohorts 1 and 2 only: Participant must be healthy on the basis of clinical laboratory tests performed at screening. If the results of the laboratory screening tests are outside the laboratory normal reference ranges and additionally within the limits of toxicity Grade 2 according to the US FDA toxicity tables (ie, for tests in the FDA tableb), the participant may be included only if the investigator judges the abnormalities or deviations from normal to be not clinically significant and appropriate and reasonable for the population under study. This determination must be recorded in the participant's source documents and initialed by the investigator.

*Note: If laboratory screening tests are out of laboratory normal ranges and deemed clinically significant, repeat of screening tests is permitted once, using an unscheduled visit during the screening period to assess eligibility. Screening laboratory tests are to be done within 28 days of randomization.*

---

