### **8.2.3. Clinical Safety Laboratory Assessments**

For participants in Cohorts 1 and 2, blood samples for serum chemistry and hematology will be collected at screening, on Day 1, and 7 days after vaccination (or at the exit visit if early exit is within 7 days after vaccination and the participant terminates from the study without withdrawing consent) as noted in [Appendix 2: Clinical Laboratory Tests](#). The investigator must review the laboratory results, document this review, and record any clinically relevant changes occurring during the study in the AE section of the eCRF. The laboratory reports must be filed with the source documents.

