### **AESIs**

TTS is considered to be an AESI. Thrombotic events and/or thrombocytopenia (defined as platelet count below the lower limit of normal [LLN] range for the testing laboratory) are considered to be potential AESIs. All AESIs, including potential AESIs, will be reported to the sponsor from the moment of study vaccination until 6 months after the study vaccination (see Section 8.3.6).

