### 8.3.6.1. Thrombosis with Thrombocytopenia Syndrome

As described in Section 2.2, TTS has been observed following vaccination with Janssen COVID vaccine and is considered to be an AESI in this study. TTS is a syndrome characterized by a combination of both a thrombotic event and thrombocytopenia. ([American Society of Hematology 2021](#); [Brighton Collaboration 2021](#))

Because this syndrome is rare and not completely understood, all cases of thrombosis and/or thrombocytopenia will be considered a potential case of TTS and should be reported to the sponsor within 24 hours of awareness using the AESI form. Each potential AESI will be reviewed to identify a TTS case. A potential TTS case is defined as:

- Thrombotic events: suspected deep vessel venous or arterial thrombotic events as detailed in Section 10.7, [Appendix 7](#), and/or
- Thrombocytopenia, defined as platelet count below LLN for the testing laboratory

Symptoms, signs, or conditions suggestive of a thrombotic event or thrombocytopenia should be recorded and reported as a potential AESI even if the final or definitive diagnosis has not yet been determined, and alternative diagnoses have not yet been eliminated or shown to be less likely. Follow-up information and final diagnoses, if applicable, should be submitted to the sponsor as soon as they become available.

In the event of thrombocytopenia, study site personnel should report the absolute value for the platelet count and the reference range for the laboratory test used.

For either a thrombotic event or thrombocytopenia, complete blood count including platelet count and a coagulation profile available from participant's medical records should be entered in the eCRF. In case these results are not available at the time of the event report in the eCRF, the study site is required to obtain a complete blood count including platelet count and a coagulation profile. Tests should be performed at the local laboratory. Repeat testing may be requested for confirmation upon sponsor discretion.

Aliquots of serum samples collected for immunogenicity test can be reconverted for participant's safety purposes upon sponsor request.

Refer to [Appendix 2, Table 20](#) for a non-exhaustive list of required tests.

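### The SAP's programmed search for potential AESIs reads only reported AE terms, so it does not apply the protocol's platelet-count definition of thrombocytopenia to the Day 8 laboratory data

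*SAP*

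**What the plan says.** **Definition.** Protocol 8.3.6.1 gives, as one of the two criteria for a potential TTS case, "Thrombocytopenia, defined as platelet count below LLN for the testing laboratory". Protocol 8.3.1 uses the same cut-off when it names the potential AESIs: "Thrombotic events and/or thrombocytopenia (defined as platelet count below the lower limit of normal [LLN] range for the testing laboratory) are considered to be potential" (the sentence closes with that abbreviation). Neither place adds a grade, symptom or clinical-relevance condition.

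**Reporting duty.** Protocol 8.3.6.1 also says that "all cases of thrombosis and/or thrombocytopenia will be considered a potential case of TTS and should be reported to the sponsor within 24 hours of" the site learning of the case, on the AESI form.

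**Laboratory results in general.** Protocol 8.2.3 schedules the samples: "For participants in Cohorts 1 and 2, blood samples for serum chemistry and hematology will be collected at screening, on Day 1, and 7 days" following the dose. Table 19 puts platelet count in the hematology panel and, unlike prothrombin time and aPTT, does not limit it to baseline. The same section tells the investigator to review the results and "record any clinically relevant changes occurring during the study in the AE section of the eCRF". It does not refer to 8.3.6.1.

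**Analysis.** SAP 5.3.2.1 gives two routes into the potential-AESI tables: "In addition to the potential AESIs as identified by the investigator in the database, potential AESIs will also be selected programmatically". The second route is defined by "Those will include all reported AEs that are identified by the selection rule: SMQ (Standardised MedDRA Queries"), a thrombocytopenia sub-SMQ or one high-level term. Separately, SAP 5.7.1 summarizes and lists all laboratory abnormalities, SAP 5.7 presents such tables by cohort and arm, and SAP Appendix 2 assesses them against local normal ranges as well as FDA grades.

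**The concern.** The protocol defines thrombocytopenia by a measured value. The SAP's programmed route finds it only when someone has already written it down as an adverse event. A programmed search that supplements investigator flags is most useful where flagging is incomplete. For a low platelet count with no AE entry, it returns nothing, even though the value and the local range are in the data.

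Under-reporting is plausible because two protocol sections give different triggers. A site working from 8.2.3 may judge a mildly low Day 8 count not clinically relevant and enter nothing. A site working from 8.3.6.1 would report the same count within 24 hours. The thrombocytopenia rows, shown by arm and post-dose interval, would then partly reflect site reporting habits.

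This matters because potential AESIs are the pool reviewed for TTS, and because protocol 4.3 says that Ad26 up to 2×10^11 vp is evaluated for the first time here and that safety will be monitored closely.

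**Working it through.** The documents give no figure to reproduce on this point. The check is mainly a comparison of text, with arithmetic only for scale.

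**1. Can an unflagged low count enter the potential-AESI tables?**
- Investigator route (SAP 5.3.2.1, 5.3.2.2): requires a flag from the site. No flag, no entry.
- Programmed route (SAP 5.3.2.1): requires a reported AE whose coded term falls in the listed groupings. No AE, no entry.
- Laboratory route (SAP 5.7.1, Appendix 2): the value is read and compared with the local range, but nothing in the SAP passes the result to the potential-AESI tables.

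So a count that is neither flagged nor entered as an AE is absent from those tables and present in the laboratory tables.

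**2. Would FDA grades be enough for a laboratory rule?** No. In protocol Appendix 6, Grade 1 platelet decrease is 125,000 to 140,000. A count above 140,000 but below a higher local LLN has no grade yet meets the protocol definition. The rule must use the local LLN, which SAP Appendix 2 already brings into the analysis.

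**3. Who is affected?** Scheduled safety laboratory tests are in Cohorts 1 and 2 only (protocol 8.2, 8.2.3).
- Planned number: 132 + 528 = 660, or 12 + 48 = 60 per arm.
- There is one scheduled post-vaccination count, at Day 8 (+3 days), so every scheduled value falls in the 0–28 day interval of SAP 5.3.2.3.

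**4. How many low counts?** The documents give no below-LLN rate, so the rate r is an assumption. The expected number in 660 is 660 × r. The chance of at least one in an arm of 60 is 1 − (1 − r)^60.

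| Assumed r | Expected in 660 | At least one in an arm of 60 |
|---|---|---|
| 0.5% | 3.3 | 26.0% |
| 1% | 6.6 | 45.3% |
| 2.5% | 16.5 | 78.1% |
| 5% | 33 | 95.4% |

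The first three percentages agree with the N=60 column of protocol Table 15, which applies the same formula to AE rates.

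**5. How many would be missed?** Expected missed = 660 × r × u, where u is the share of low counts that sites neither flag nor enter as AEs. The documents say nothing about u. At u = 0 (full compliance with 8.3.6.1) the number is 0; at u = 1 it equals the second column. That column is therefore an upper bound at each assumed rate.

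**6. Is baseline status relevant?** Inclusion criterion 6 admits participants whose screening values are out of range and "additionally within the limits of toxicity Grade 2 according to the US FDA toxicity tables", if the investigator judges them not clinically significant. For platelets, Appendix 6 gives Grade 2 as 100,000 to 124,000. Some Day 8 counts below LLN may therefore be continuations of a low baseline.

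**The case against.** The strongest reply is that the protocol already closes the gap. Section 8.3.6.1 is unconditional, 8.3.6 requires potential AESIs to be reported irrespective of seriousness or causality, and Appendix 4 includes laboratory abnormalities in the AE definition. Section 8.2.3 says what to record but exempts nothing from AESI reporting. A reader might infer that a mildly low Day 8 count may properly stay out of the reports; the documents do not support that. An unreported count would be a site departure from the protocol. This part of the reply stands. It does not show that departures will be rare, since 8.2.3 gives a narrower trigger with no cross-reference.

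The second reply is that the SAP never says the programmed search is meant to find unreported laboratory values. It still catches events that were reported as AEs but not flagged. This also stands: the search does what its text says, but does not apply the protocol's definition.

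Third, a reader might infer that low counts are lost or that differences between arms cannot be seen. That is not so. The laboratory tables show abnormalities by arm against local ranges, so the loss is confined to the potential-AESI tables.

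Fourth, a reader might infer that the primary AESI endpoint is miscounted. The AESI is TTS, which needs thrombosis together with thrombocytopenia. An isolated low count is only a potential AESI, and committee review of reported cases decides whether TTS occurred.

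Finally, raw values have no preferred term, no investigator relatedness and no start and end dates, so they do not fit the existing table rules. This affects the cost and form of the fix, not the need for it.

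**Conclusion.** The mismatch is real and limited. The protocol's cut-off is a laboratory value, and no route into the SAP's potential-AESI tables reads that value. A Day 8 count below LLN in Cohorts 1 and 2 is missing from those tables if the site neither flags it nor enters it as an AE.

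The size cannot be fixed from the documents. About 3 to 33 of 660 participants would have a low Day 8 count at assumed rates of 0.5% to 5%, taking the planned enrolment and a Day 8 sample from everyone. It would be wrong to read these as missed cases: they are all low counts, and with full reporting none would be missed.

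Cohorts 3 and 4 have no scheduled platelet counts and are outside the point, apart from any unscheduled results. This is a worthwhile, inexpensive improvement to a secondary check. It is not a fault that undermines the safety analysis.

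**What to change.** 1. **SAP 5.3.2.1:** add a laboratory-based programmed selection, namely any post-vaccination platelet count below the testing laboratory's LLN. Use the local LLN, not the FDA grade.
2. **Presentation:** show it by arm and post-dose interval, as a separate row or table next to the term-based potential AESIs. Allocate by sample date and count each participant once per interval. Do not apply preferred-term, relatedness or event-combining rules to raw values.
3. **Baseline split:** separate participants whose baseline count (SAP 5.1.1) was at or above LLN from those already below it.
4. **Reconciliation:** before database lock, compare this list with the reported potential AESIs and query the differences with the sites.
5. **Protocol:** reconcile 8.2.3 with 8.3.6.1, so that sites know how the instruction on clinically relevant changes relates to the rule on counts below LLN.

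The platelet values and local ranges are already collected, so no new sampling is needed. The cost is a short derivation rule, one extra row or table, some queries, and a longer list of mostly benign counts. The baseline split makes that list easier to read. The selection at analysis supplements the 24-hour report and does not replace it.

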### **5.3.2.2. Analysis of Adverse Events**

Number and percentage of participants with at least one particular AE (unsolicited/solicited) will be tabulated. Unsolicited AEs will be summarized by System Organ Class (SOC) and Preferred Term (PT).

Solicited AEs will be summarized by class (administration site, systemic) and Derived Term. The number and percentages of participants with at least one solicited local (at injection site) or systemic adverse event will be presented. For solicited AEs, the following tables will be provided: overall summary, by worst severity grade, at least grade 3, related (systemic only), time to onset (in days) and duration (in days). Note: Duration is defined as number of days from the start of the event until resolution of the event. The time to first onset is defined as date of first onset – reference date + 1. The reference date is the start date of the post-dose period. For solicited AEs, the denominator for the percentages is the number of participants with solicited event data assessed by the investigator in the considered population, phase and arm (incidence per 100 participants/phase).

A tabulation of the distribution of temperatures per half degree intervals will also be provided.

Frequencies of unsolicited AEs, separately for all and vaccination-related only, will be presented by SOC and PT. The following tables will be provided: overall summary, all AEs, most frequent AEs, AEs with at least grade 3, related AEs, AEs leading to death, AEs leading to study discontinuation, SAEs, related SAEs, potential AESIs and AESIs, COVID-19 related AEs.

AESIs, AEs flagged by the investigator as potential AESI and AESIs identified via a programmed selection will be summarized by Interest Category and PT. Denominator for the percentages is the number of participants in the considered population, phase and arm (incidence per 100 participants/phase).

Potential AESIs selected programmatically will be tabulated by categories: ‘Embolic and thrombotic events (SMQ)’ and ‘Haematopoietic Thrombocytopenias (SMQ) (broad) or HLT = Thrombocytopenias’. Potential AESI determined programmatically, related to study vaccine (investigator assessment), will be tabulated similarly.

Potential AESIs as identified by the investigator, will be tabulated by categories: ‘Embolic and thrombotic events (SMQ)’ and ‘Haematopoietic Thrombocytopenias (SMQ) (broad) or HLT =

Thrombocytopenias’, and ‘Other’. Potential AESI as identified by the investigator, related to study vaccine (investigator assessment), will be tabulated similarly.

AESIs (as confirmed by review) will be tabulated by categories: ‘Embolic and thrombotic events (SMQ)’ and ‘Haematopoietic Thrombocytopenias (SMQ) (broad) or HLT=Thrombocytopenias’.

All AESI analyses will be presented by phase as well as by time interval. The definition of the different time intervals can be found in Section 5.3.2.3.

For AESIs, potential AESIs as identified by the investigator and potential AESIs determined programmatically, attribution to the intervals will be done similarly to the unsolicited AEs as described in Section 5.3.2.3. For Step 2 of phase allocation of adverse events, the ‘0 - 28 days post-dose’ interval should be treated similar to active periods and the rest as non-active periods.

Summaries, listings, datasets, or participant narratives may be provided, as appropriate, for those participants who die, who discontinue the study vaccination due to an AE, who discontinue the study due to an AE, or who experience a severe AE, an AESI, an SAE or a COVID-19 infection.

### **5.3.2.3. Phase Allocation of Adverse Events**

As the analysis of solicited events will be based on the overall assessment of the investigator, which is documented in the CE domain, the Analysis Data Model (ADaM) dataset will be based on the CE domain. Solicited events are allocated to the phases as described below, however they are always allocated to Post-dose period and will never be attributed to the screening phase. Time of day is not considered while attributing solicited AEs to phases.

For unsolicited AEs, the steps below are followed as well.

#### **Step 1: Allocation of events to the periods:**

Adverse events in the SDTM database are allocated to periods based on their start date/time. If the start date/time of an event falls between (or on) the start and stop date/time of a period, the AE is attributed to that period (treatment-emergent principle).

- In case of partial start or stop dates (i.e., time and/or day and/or month and/or year missing), the events are allocated to the periods using the available partial information on start and end date; no imputation will be done. If, for instance, the AE start date only month and year are available, these data are compared to the month and year information of the periods. This rule may lead to multiplication of the event as a consequence of its assignment to multiple periods.
- In case of a completely missing end date, the date is imputed by the cut-off date of the analysis for participants still ongoing in the study, and by the end date of the last period for participants who discontinued or completed the trial. The imputed end dates will not be shown in the data listings.
- In case of a completely missing start date, the event is allocated to the first active phase (Post-dose period), except if the end date of the AE falls before the start of the first active phase (Post-dose period).

**Step 2: Combination of events:**

Overlapping/consecutive events are defined as events of the same participant with the same preferred term which have at least 1 day overlap or for which the start date of an event is 1 day after the end date of the preceding event. Overlapping/consecutive events may be combined into one AE or not, according to the following rules:

1. If overlapping/consecutive events start in one of the following phases/periods - Screening or Follow-up (defined as non-active periods) - followed by an AE in - Post-dose period (defined as active period) - they are allocated to their respective phases/periods and are considered as separate events.
2. In case overlapping/consecutive events start within a single period, they are considered as one and the same AE. The individual events which contribute to this AE are retained as individual records in the ADaM database but are assigned the same onset, period, and total duration. All related attributes to the AE/phase/period should also be consistent with the new event.
3. In case overlapping/consecutive events start in both an active period followed by a consecutive non-active period, they are allocated to the active period only and are considered as one and the same AE. The individual events which contribute to this AE are retained as individual records in the ADaM database but are assigned the same onset, treatment period, and total duration. All related attributes to the AE/phase/period should also be consistent with the new event.
4. In case an active period is followed by another active period, and the overlapping/consecutive events start in both periods, they are allocated to their respective period and are considered as separate AEs. In case overlapping/consecutive events start in non-consecutive periods (regardless of active or non-active), they are allocated to their respective period and are considered as separate AEs.
5. In case a non-active period is followed by another non-active period, and the overlapping/consecutive events start in both periods, they are allocated to the first period and they are considered as one and the same AE. The individual events which contribute to this AE are retained as individual records in the ADaM database but are assigned the same onset, period, and total duration. All related attributes to the AE/phase/period should also be consistent with the new event.

